### 4.5. Study Termination

The study may be discontinued at the discretion of the Investigator or Sponsor if any of the following criteria are met:

- medical or ethical reasons affecting the continued performance of the study
- difficulties in the recruitment of subjects
- cancellation of drug development

- the DMC recommends discontinuation of the study due to safety concerns.

## 5. STUDY TREATMENTS

### 5.1. Description, Storage, Packaging, and Labeling

The IMP [REDACTED] will be supplied by the Sponsor (or designee), along with the batch/lot numbers and Certificates of Analysis. The IMP will be provided as a clear and sterile solution, formulated for inhalation via InnoSpire Go nebulizer system (Philips). [REDACTED]

The bulk drug container and unit dose containers will be labeled in accordance with national laws and regulations and packaged together with the diluent as kit boxes. Study treatment (IMP or placebo) will be prepared for administration by qualified site personnel in accordance with [Table 5](#).

**Table 5: Preparation of TRK-250 Doses for Nebulization**

Dose	2 mg (or Placebo)	10 mg (or Placebo)	30 mg (or Placebo)	60 mg (or Placebo)
[REDACTED]	[REDACTED]	[REDACTED]	[REDACTED]	[REDACTED]
[REDACTED]	[REDACTED]	[REDACTED]	[REDACTED]	[REDACTED]

### 5.2. Study Treatment Administration

Each dose of TRK-250 and placebo will be administered by oral inhalation using InnoSpire Go. Measures to protect against secondary exposure will be employed as described in [Section 5.2.1](#).

Study treatment must be administered by blinded site personnel.

Subjects will be administered the study treatment in a sitting position. All doses will be administered irrespective of fasting status.

Subjects must be instructed not to disclose to anyone whether the study treatment is associated with a taste or odor.

Prior to administering study drug, the Investigator should passively observe the subject’s cough character and frequency to establish a “qualitative” baseline. The subject should be asked to rate informally her/his shortness of breath (eg, on a scale of 0 to 10 or none, mild, moderate, or severe).

After starting study drug administration and for roughly 30 minutes afterwards, the Investigator should continue to passively observe the subject for change in character and/or

frequency of cough. Special attention should be given to assessing whether the subject's cough may impede proper study treatment.

The same informal self-assessment should be performed for chest tightness. A substantial fraction of patients experience no change in cough or chest tightness during methacholine or histamine challenge even with  $\geq 20\%$  decline in FEV1, but a change in cough and/or chest tightness are good and early indicators of worsening bronchoconstriction.

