### 5.4. Blinding

The following controls will be employed to maintain the double-blind status of the study:

- The placebo solution will be identical in appearance to TRK-250.
- The Investigator and other site personnel not involved in the preparation of study treatment will remain blinded to study treatment randomization.
- Respiratory protection must be used (as described in [Section 5.2.1](#)) during study treatment administration to prevent site personnel from detecting any taste or odor of the study treatment.
- Subjects must be instructed not to disclose to anyone whether study treatment is associated with a taste or odor.
- Interim bioanalytical data will be provided in a blinded manner.

The IxRS will be programmed with blind-breaking instructions. The study blind may be broken if, in the opinion of the Investigator, it is in the subject's best interest to know the study treatment assignment. Whenever possible, and providing it does not interfere with or delay any decision in the best interest of the subject, the Investigator will discuss the intended code-break with the Sponsor. If it becomes necessary to break the code during the study, the date, time, and reason will be recorded in the subject's source data and CRF, as appropriate.

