## 7.1. Safety and Tolerability Assessments

### 7.1.1. Adverse Events

AE definitions, assignment of seriousness, severity, and causality, and procedures for reporting SAE are detailed in [Appendix 1](#).

The condition of each subject will be monitored from the time of signing the ICF to final discharge from the study. Subjects will be observed for any signs or symptoms and asked about their condition by open questioning, such as “How have you been feeling since you were last asked?”, at least once each day while resident at the study site and at each study visit. Subjects will also be encouraged to spontaneously report AE occurring at any other time during the study.

All nonserious AE, whether reported by the subject voluntarily or upon questioning, or noted on physical examination, will be recorded from initiation of study drug until study completion. SAE will be recorded from the time the subject signs the ICF until study completion. The nature, time of onset, duration, seriousness, and severity will be documented, together with an Investigator’s opinion of the relationship to study drug.

SAE will be followed up until the subject’s status reverts to baseline, the AE is determined by the Investigator to be irreversible, or death of the subject. Non-serious AE will be followed up until resolution or the AE is determined by the Investigator to be irreversible. This will be completed at the Investigator’s discretion. If not possible to follow up an SAE or AE, appropriate reasons should be provided.

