## 10. APPENDICES

## Appendix 1: Adverse Event Reporting

### Definitions

An adverse event (AE) is any untoward medical occurrence in a subject or clinical investigation subject administered a pharmaceutical product, which does not necessarily have a causal relationship with this treatment. An AE can therefore be any unfavorable and/or unintended sign (including an abnormal laboratory finding), symptom, or disease temporally associated with the use of a study drug in humans, whether or not related to the study drug.

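### The instruction not to disclose a taste or odor has no exception for adverse events, so unpleasant taste or smell AEs may be under-reported

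*Protocol*

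**What the plan says.** The instruction appears twice in the protocol. Section 5.2 (Study Treatment Administration) states: "Subjects must be instructed not to disclose to anyone whether the study treatment is associated with a taste or odor". Section 5.4 (Blinding) lists it again among the controls that keep the study double-blind: "Subjects must be instructed not to disclose to anyone whether study treatment is associated with a taste or odor". Both are mandatory, both cover every possible listener, and neither makes an exception for adverse events or names a person who may receive such a report.

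The same list in Section 5.4 calls for respiratory protection "to prevent site personnel from detecting any taste or odor of the study treatment". On matching, it says: "The placebo solution will be identical in appearance to TRK-250". The visible text makes no statement about matching for taste or odor.

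AE collection is set out in Section 7.1.1: "Subjects will be observed for any signs or symptoms and asked about their condition by open questioning". It continues: "Subjects will also be encouraged to spontaneously report AE occurring at any other time during the study". On recording: "All nonserious AE, whether reported by the subject voluntarily or upon questioning, or noted on physical examination, will be recorded". Appendix 1 gives the definition: "An AE can therefore be any unfavorable and/or unintended sign (including an abnormal laboratory finding), symptom, or disease temporally associated" with use of the study drug, whether or not it is judged related.

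AE incidence and severity is one of the primary endpoints (Section 2.2.1). SAP Section 10.6.1 tabulates TEAEs by treatment, system organ class and preferred term. SAP Section 7 sets each TRK-250 dose beside a pooled placebo column within each part. The SAP does not mention taste or smell reports.

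**The concern.** Taste and smell are known only to the subject. Observation, laboratory tests, oximetry and spirometry will not reveal that an inhaled solution left a foul or lingering taste. The subject's own account is the only source for such an event, and it is the account that Sections 5.2 and 5.4 restrict.

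This is the first administration of TRK-250 to humans, by inhalation, with safety and tolerability as the primary objective. An event that is never mentioned leaves no record and is counted as no event. A zero in a taste or smell row could then mean that nobody was troubled, or that troubled subjects did as they were told. The tables could not distinguish the two.

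**Working it through.** The plan has no figure to reproduce here: it gives no rate for such events, and Section 8.1 states no formal sample-size calculation. The check is mainly a comparison of texts.

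**Step 1: does such an event meet the AE definition?** Appendix 1 begins by requiring an untoward occurrence and then includes unfavorable or unintended symptoms linked in time to the drug. Merely noticing a taste while inhaling need not be untoward. An unpleasant or persistent taste or smell that troubles the subject is an unfavorable symptom after dosing, so it qualifies.

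**Step 2: what must happen to it?** Under Section 7.1.1 the subject is asked openly, is encouraged to volunteer it, and the nonserious AE is recorded from the start of study drug.

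**Step 3: what do Sections 5.2 and 5.4 tell the subject?** To tell nobody whether the treatment has a taste or odor. A subject who reports that the inhaled dose left a bad taste has disclosed exactly that. The duties in steps 2 and 3 cannot both be met literally, and no visible text in Section 7.1.1, Appendix 1 or the SAP says which prevails.

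**Step 4: direction of the effect.** Let p be the true proportion of subjects in an arm with such an AE, and c the share still reported under the instruction. The expected observed proportion is p × c.

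- Only one arm has a taste or odor: the true difference is p − 0 = p and the expected observed difference is p × c − 0. It shrinks toward zero by the factor c, whichever arm it is.
- Both arms alike, with the same c: the difference stays at zero, and both columns are under-counted.
- Neither arm: nothing is lost.

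**Step 5: illustration of size.** The chance of at least one recorded event among n subjects is 1 − (1 − p × c)^n. Arm sizes come from Sections 3.1.1 and 3.1.2: 3 active per Part A cohort, 4 active per Part B cohort, and 12 active per part (4 × 3 = 12; 3 × 4 = 12). Both p and c are assumptions. The entries use p = 25%, with the range for p = 10% to 50% in brackets.

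| n active | c = 1 | c = 0.5 | c = 0.2 | c = 0 |
|---|---|---|---|---|
| 3 | 58% (27% to 88%) | 33% (14% to 58%) | 14% (6% to 27%) | 0% |
| 4 | 68% (34% to 94%) | 41% (19% to 68%) | 19% (8% to 34%) | 0% |
| 12 | 97% (72% to >99%) | 80% (46% to 97%) | 46% (22% to 72%) | 0% |

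For example, with n = 12, p = 0.25 and c = 0.5: 1 − (1 − 0.125)^12 = 0.799. The n = 12 row applies one rate to all doses in a part, although the SAP lists each dose separately. The table shows that the loss is graded and depends wholly on c. It does not estimate the loss in this trial.

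**The case against.** The strongest defense is that the instruction concerns a property of the product and serves the blind. On that view it can be read together with Section 7.1.1: do not discuss what the solution tastes like, but do report feeling unwell. Nothing says that Section 5.2 overrides Section 7.1.1, and any event that is mentioned must still be recorded. This is a fair reading and probably the intended one. It limits the loss to subjects who take the words at face value, but the words given to subjects contain no such distinction.

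Three stronger inferences are tempting, and the documents do not support them.

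- **That local tolerability as a whole is silenced.** Cough, shortness of breath, chest tightness, nausea and throat irritation are outside the wording. Section 5.2 also has the first three observed or self-rated around dosing, and Section 7.1.8 recommends four postdose spirometry sessions.
- **That the TRK-250 columns are biased in its favor.** No visible text says that TRK-250, placebo or either has a taste or odor. The reference in Section 5.4 to any taste or odor is precautionary. Product details in Section 5.1 are partly redacted, so taste matching may be described there.
- **That every such event is lost.** This assumes complete literal compliance. With half still reported and an assumed rate of 25%, the chance of at least one record in 12 subjects is 80%, against 97% with full reporting.

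An exception for AEs could also stand in redacted text or in a separate site document. None is referenced.

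**Conclusion.** The conflict between Sections 5.2 and 5.4 on one side and Section 7.1.1 with Appendix 1 on the other is real and can be read from the text. Its consequence is conditional: AEs of unpleasant or persistent taste or smell may be under-counted to the extent that subjects follow the instruction literally. If only one arm has a taste or odor, the comparison of those rows with pooled placebo is biased toward no difference. The size cannot be stated, because the documents give neither an event rate nor a compliance rate. The effect is confined to these rows. It is worth correcting because these events feed a primary endpoint in a first-in-human inhaled study and have no other source.

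**What to change.** Keep the instruction for casual disclosure, such as remarks to other subjects or comments during dosing. Add to both Section 5.2 and Section 5.4, and to the instructions given to subjects, wording such as: This instruction does not limit adverse event reporting; any unpleasant, altered or persistent taste or smell that troubles the subject is to be reported to the Investigator and recorded as an AE under Section 7.1.1.

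Reports should go to the Investigator, not to the staff who prepare treatment. Section 5.4 does not require preparation staff to stay blinded, while Section 7.1.1 and Appendix 1 give the severity and causality assessments to the Investigator. A detour through preparation staff would add potentially unblinded AE collection and still bring the information back to the blinded assessor.

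The drafting cost is a short addition in two places. The real cost is to the blind: a taste report may occasionally hint at allocation to the Investigator, and with 3 active and 1 placebo per Part A cohort, differing reports could suggest the allocation of the others. That is a modest price for being able to interpret a zero in these rows. No dose, schedule or clinical rule changes.

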### 5.2.1. Secondary Exposure Protection Measures

Study treatment may be administered in a negative pressure enclosure or in proximity to a portable high efficiency particulate air (HEPA) filtration system intended for healthcare in accordance with local standard operating procedures (SOP) and/or study documents.

### 5.3. Randomization

Randomization to placebo/active will be performed using an interactive voice/web response system (IxRS) randomization service. Investigators must register the subject for the IxRS system in sequence of the screening completion and dispense study drug to each subject per the code allocated by IxRS. This unique drug code will not be changed throughout the study.

### 5.4. Blinding

The following controls will be employed to maintain the double-blind status of the study:

- The placebo solution will be identical in appearance to TRK-250.
- The Investigator and other site personnel not involved in the preparation of study treatment will remain blinded to study treatment randomization.
- Respiratory protection must be used (as described in [Section 5.2.1](#)) during study treatment administration to prevent site personnel from detecting any taste or odor of the study treatment.
- Subjects must be instructed not to disclose to anyone whether study treatment is associated with a taste or odor.
- Interim bioanalytical data will be provided in a blinded manner.

The IxRS will be programmed with blind-breaking instructions. The study blind may be broken if, in the opinion of the Investigator, it is in the subject's best interest to know the study treatment assignment. Whenever possible, and providing it does not interfere with or delay any decision in the best interest of the subject, the Investigator will discuss the intended code-break with the Sponsor. If it becomes necessary to break the code during the study, the date, time, and reason will be recorded in the subject's source data and CRF, as appropriate.

### **5.5. Treatment Compliance**

To ensure treatment compliance, all doses of study treatment will be administered under the supervision of suitably qualified site personnel.

### **5.6. Drug Accountability**

The Investigator will maintain an accurate record of receipt of study supplies. In addition, an accurate drug disposition record will be kept, specifying the amount dispensed to each subject and the date of dispensing. This drug accountability record will be available for inspection at any time. At the completion of the study, the original drug accountability record will be available for review by [REDACTED] or the Sponsor on request.

For each batch of unit doses, the empty used unit dose containers will be discarded upon satisfactory completion of the compliance and accountability procedures. Any unused assembled unit doses will be retained until completion of the study.

At the completion of the study, all unused supplies will be returned to [REDACTED] (or designee) or may be destroyed at the study site in accordance with [REDACTED] or the Sponsor's written instructions and local SOP.

## **6. CONCOMITANT THERAPIES AND OTHER RESTRICTIONS**

### **6.1. Concomitant Therapies**

#### **6.1.1. Restricted Concomitant Therapies**

Subjects should be instructed to withhold for at least 4 hours before planned study visits **any short-acting** bronchodilator therapy (beta-agonist or anticholinergic agents). Withheld doses may be taken after the spirometry session scheduled to occur within 30 minutes after completion of study treatment administration.

Each subject will refrain from use of any new prescription or nonprescription medications during enrollment until the last planned or unscheduled study visit, unless clinically indicated to safeguard the subject's safety or well-being.

Either pirfenidone or nintedanib must have been taken at a stable dose for at least 4 weeks prior to Screening and should be continued at the same dose throughout a subject's enrollment (ie, from signing the ICF to the last protocol-specified assessment, whether scheduled or unscheduled). Dose adjustment in accordance with the prescribing information is permitted if clinically indicated.

All other therapies are permitted concomitant therapies. All prescription medications should be continued at the same dose throughout a subject's enrollment (ie, from signing the ICF to the last protocol-specified assessment, whether scheduled or unscheduled), unless a change is clinically indicated to safeguard the subject's safety or well-being. Consistent compliance and dosing of inhaled therapies is particularly important.

Any medication taken by a subject during the course of the study and the reason for its use will be documented in the source data and in the relevant CRF.

### **6.1.2. Prohibited Concomitant Therapies**

Taking pirfenidone and nintedanib simultaneously is prohibited for subjects enrolled in this study.

Taking a systemic corticosteroid, cytotoxic therapy (eg, chlorambucil, azathioprine, cyclophosphamide, or methotrexate), vasodilator therapy for pulmonary hypertension (eg, bosentan), unapproved treatment for IPF (eg, interferon-gamma, penicillamine, cyclosporine, mycophenolate, or N-acetylcysteine), or any other investigational treatment is prohibited for subjects enrolled in this study.

### **6.2. Diet**

While confined at the study site, subjects will receive a standardized diet at scheduled times that do not conflict with other study-related activities. Subjects will be fasted overnight (at least 8 hours) before collection of blood samples for safety laboratory tests.

On the days with PK assessments (Day 1 for Part A and Days 1 and 22 for Part B), meals will be identical for each cohort.

Water will be freely available at all times.

Consumption of alcohol >21 units per week for males and >14 units per week for females is not permitted within 30 days prior to Screening until the end of the subject's enrollment. One unit of alcohol equals 12 oz (360 mL) beer, 1½ oz (45 mL) liquor, or 5 oz (150 mL) wine.

### **6.3. Smoking**

Subjects may not consume in any form tobacco- or nicotine-containing products, excluding over-the-counter or prescription nicotine replacement products approved for marketing by the FDA, within 3 months prior to Day 1 until the end of the subject's enrollment.

### **6.4. Blood Donation**

Subjects must not donate blood, plasma, or platelets from 6 weeks prior to Day 1 until 56 days after the end of the subject's enrollment.

### **6.5. Contraception**

Women who are not of childbearing potential will not be required to use contraception. Women not of childbearing potential are defined as:

- permanently sterile due to hysterectomy or bilateral oophorectomy confirmed by history, or
- postmenopausal, defined as at least 12 months postcessation of menses without an alternative medical cause, confirmed by a Screening blood follicle-stimulating hormone level >40 mIU/mL.

Subjects who are WCBP must be willing to use a highly effective method of birth control (ie, contraceptive measure with a failure rate of <1% per year) in conjunction with male barrier contraception (ie, male condom with spermicide) from the time of signing the ICF until 90 days after the last dose of study treatment. The highly effective method of contraception should be started at least 1 menstrual cycle prior to the first dose of study drug. Highly effective methods of contraception are:

- intrauterine device (IUD; eg, Mirena®). Steel or copper IUDs are not acceptable.
- established use of oral, implantable, transdermal, or injectable hormonal method of contraception associated with inhibition of ovulation.
- male sterilization (performed at least 90 days prior to the Screening visit), with verbal confirmation of surgical success (for female subjects on the study, the vasectomized male partner should be the sole partner for that subject).
- bilateral salpingectomy, tubal ligation, or tubal occlusion (performed at least 90 days prior to the Screening visit).

Male subjects will be surgically sterile for at least 90 days prior to Screening or will be required to use a male condom with spermicide from Day 1 until 90 days after the last dose of study drug when sexually active with female partners of childbearing potential. Sexual intercourse with female partners who are pregnant or breastfeeding should be avoided unless condoms are used from the time of the first dose until 90 days after the last dose of study drug. Male subjects are required to refrain from donation of sperm from Day 1 until 90 days after the last dose of study drug.

Subjects who practice true abstinence, because of the subject's lifestyle choice (ie, the subject should not become abstinent just for the purpose of study participation), are exempt from contraceptive requirements. Periodic abstinence (eg, calendar, ovulation, symptothermal, postovulation methods) and coital withdrawal are not acceptable methods of contraception. If a subject who is abstinent at the time of signing the ICF becomes sexually active she/he must agree to use contraception as described previously.

For subjects who are exclusively in same-sex relationships, contraceptive requirements do not apply. If a subject who is in a same-sex relationship at the time of signing the ICF becomes heterosexually active, they must agree to use contraception as described above.

